Study protocol

Introduction

The study will be a multicenter, randomized, double-blind, follow-up clinical trial.

Neither the examining doctor nor the patient knows which capsule they will receive. Just the test unlock the codes after completion. The randomization was performed externally, not included in the study

performed by a person.

Number of patients: a total of 105 patients / 21-21 per clinic

(with 7 patients each in three treatment groups)

Three treatment groups

- 35 people physical therapy + Loxacon
- 35 main physical therapy + Placebo
- 35 people only for physical therapy

Physiotherapy takes place according to a uniform protocol.

Physiotherapy 2x30 minutes per week for 5 weeks (10 times in total).

The course of the investigation

1st visit: selection, filling in questionnaires

2nd visit: after the 10th exercise session, while taking Loxacon/placebo, filling in questionnaires

3rd visit: Uniformly after another 2 months of taking Loxacon, in all three groups, completing questionnaires

After the first 5 weeks, all three branches will receive enough Loxacon capsules for 2 months!

The parameters to be tested

- WOMAC test
- VAS test
- EQ-5D-5L quality of life test
- Goniometer angle measurement(ROM)

The test is completed by patients who participated in more than 70% of the treatment!

Monitoring of side effects

It is the duty of the doctor of the given center - who reports to the investigator.

2

Pain reliever use

If it is necessary to take painkillers, paracetamol can be used uniformly, which is recorded.

The primary research objective:

How does Loxacon - as a dietary supplement - capsule work in osteoarthritis of the knee joint on the pain and function of patients with

The secondary research objective:

How Loxacon capsules work for patients with knee osteoarthritis
quality of life?

SELECTION CRITERIA

1. According to the ACR (American College of Rheumatology) knee arthrosis criteria, knee arthrosis supported by an imaging procedure (comparative knee X-ray). Both in the case of knee involvement, the more complaining knee will be examined!
2. A patient reporting knee pain characteristic of knee arthrosis for at least 3 months, where the VAS value 40-70 mm.
3. With a diagnosis of mild and moderate knee arthrosis.
4. Male or female patients between the ages of 40 and 80.
5. With a BMI between 25-35.

EXCLUSION CRITERIA

- Intra-articular corticosteroid within 3 months before starting treatment injection.
- Intra-articular hyaluronic acid treatment within 6 months or such treatment during the examination

treatment.

- Physiotherapy treatment received within 3 months prior to the start of the treatment.

- NSAID changed within 3 months prior to treatment or during treatment, or

chondroprotective treatment.

- In inflammatory rheumatological diseases (RA, SPA, APs, crystal arthropathies, etc.)

suffering patient.

- Knee surgery within 6 months prior to the examination.

- Presence of a metal implant in the knee joint.

- Any patient with a knee fracture.

- Patients who had a knee joint injury within 6 months prior to the examination.

- Patients with a palpable fluid collection in the knee or Baker's cyst.

- Uncooperative patients, patients with inadequate mental or psychological status.

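### A participation threshold placed under the outcome list may leave some randomised patients unmeasured, and the treatment it refers to is not defined

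*Protocol*

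**What the plan says.** The protocol describes a randomised trial with three arms of 35: physiotherapy with Loxacon, physiotherapy with placebo, and a third arm given as "35 people only for physical therapy". Physiotherapy follows one uniform scheme of ten sessions over five weeks.

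Under The parameters to be tested, after WOMAC, VAS, EQ-5D-5L and goniometry, comes the sentence "The test is completed by patients who participated in more than 70% of the treatment".

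The visits are set out separately under The course of the investigation: "2nd visit: after the 10th exercise session, while taking Loxacon/placebo, filling in questionnaires" and "3rd visit: Uniformly after another 2 months of taking Loxacon, in all three groups, completing questionnaires". Neither visit carries a participation condition. Between them, "After the first 5 weeks, all three branches will receive enough Loxacon capsules for 2 months".

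The word test also appears in the Introduction in another sense: "Just the test unlock the codes after completion".

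**The concern.** Participation is known only once treatment is under way, so the threshold acts after randomisation. Because the sentence follows the outcome list, its natural reading is that only patients above 70% complete the outcome measures. No statement provides for measuring the others. If they are not measured, the compared groups are no longer the randomised groups. A later choice of analysis set cannot undo that, because the data would not exist.

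The threshold also has no denominator. Treatment could mean the ten sessions, the capsules of the first five weeks, the later two months of Loxacon, or a combination. The physiotherapy-only arm takes no capsule before Visit 2, so a capsule-based rule could not be applied to it up to then. Centres could apply the sentence in different ways.

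**Working it through.** **Sample size (from the Introduction).** 105 / 21 = 5 clinics; 5 × 7 = 35 per arm; 3 × 35 = 105. The stated figures agree. No alpha, power, effect size, SD or adherence rate is given, so every rate and correlation below is an assumption.

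**What the threshold means.**
- If treatment means the ten sessions: 0.70 × 10 = 7, so more than 70% means at least 8 sessions, and a patient with exactly 7 fails. The rule is then the same in all three arms.
- If treatment includes capsules: the physiotherapy-only arm has no capsule denominator before Visit 2, so the rule cannot be the same in all arms.

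**Bias if patients at or below the threshold are not measured.** Assume no true effect and a normally distributed tendency to participate that has correlation ρ with the outcome. If the lowest share e is excluded, the mean of those retained shifts by ρ × λ(e) SD, where λ(e) = φ(z_e) / (1 − e) and z_e is the e-quantile of the standard normal.
- λ(0.05) = 0.1031 / 0.95 = 0.109
- λ(0.10) = 0.1755 / 0.90 = 0.195
- λ(0.18) = 0.2624 / 0.82 = 0.320
- λ(0.20) = 0.2800 / 0.80 = 0.350

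The bias is the difference of the shifts between two arms. Type I error is from 40,000 simulated trials with 35 per arm and a pooled t-test at two-sided 5%.

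| Excluded, arm 1 / arm 2 | Correlation | Bias | Type I error |
|---|---|---|---|
| 18% / 18% | 0.5 in both | 0 | nominal (4.9%) |
| 18% / 18% | 0.5 and 0.2 | (0.5 − 0.2) × 0.320 = 0.10 SD | not quoted |
| 10% / 20% | 0.3 in both | 0.3 × (0.350 − 0.195) = 0.05 SD | about 5.4% |
| 5% / 20% | 0.5 in both | 0.5 × (0.350 − 0.109) = 0.12 SD | about 7.6% |

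Equal exclusion alone does not guarantee zero bias; the correlation with outcome must also be equal.

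**Loss of patients if only sessions count.** Assume each of ten sessions is attended independently with probability p. The excluded share is P(X ≤ 7) for a binomial(10, p) count.
- p = 0.90: 1 − (0.1937 + 0.3874 + 0.3487) = 0.070, or 7%
- p = 0.85: 1 − (0.2759 + 0.3474 + 0.1969) = 0.180, or 18%

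**Power, two arms, two-sided 5%.** Noncentral t with noncentrality d√(n/2), at d = 0.68 SD, the difference that 35 per arm detects with 80% power. This is not a protocol target.
- n = 35: 0.68 × √17.5 = 2.84, power 80%
- n = 35 × 0.93 = 32.55: 0.68 × √16.275 = 2.74, power about 77%
- n = 35 × 0.82 = 28.7: 0.68 × √14.35 = 2.58, power about 72%

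**The case against.** The strongest reply is that the harm hangs on one reading of a sentence that looks translated. The word test is not stable in this document: in "Just the test unlock the codes after completion" it cannot mean the questionnaires. The sentence may therefore only say who counts as having completed the trial. The visits, where assessments are ordered, set no participation condition. On that reading nobody is shown to go unmeasured, and what remains is the choice of main analysis set, which is commonly left to an analysis plan. This stands, and it is why the harm is stated conditionally. It does not remove the point: the natural reading remains open, Visit 3 speaks of the three groups and not of every patient, and unmeasured outcomes cannot be recovered.

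It is also fair that no bias is demonstrated. If treatment means the uniform sessions, the rule is identical in all arms, and the mild scenario barely moves the type I error. The figures show what could happen under stated assumptions, not what will.

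A reader might infer that the comparison of Loxacon with placebo is biased. The document does not support that. Under "The study will be a multicenter, randomized, double-blind, follow-up clinical trial", those two arms take capsules that patient and doctor cannot tell apart, with the same physiotherapy, and nothing suggests a large difference in exclusion between them.

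**Conclusion.** The point holds as a conditional defect of wording. As placed, the sentence can be followed so that randomised patients at or below 70% are not measured, no other statement prevents this, and its denominator is undefined.

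If it is followed that way, precision is lost at any level of exclusion: power falls from 80% to about 77% or 72% under the two attendance assumptions. Bias arises only if the excluded share, or its correlation with outcome, differs between arms. It ranges from 0 to about 0.12 SD in the scenarios shown. The main exposure is in comparisons with the physiotherapy-only arm, which takes no capsule before Visit 2 and so cannot be blinded then.

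One should not conclude that the protocol definitely bars non-adherers from assessment, or that it restricts the comparison to completers; it says neither outright. The importance lies between a minor clarification and a change that should be made, with medium confidence.

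**What to change.** Replace the sentence with: *Outcomes are collected at Visits 2 and 3 for all randomised patients whatever their participation, and the main comparison analyses them in their allocated arm.*

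Keep the set above 70% only as a supportive analysis, with treatment defined. If the definition includes capsules, note that before Visit 2 this set compares like with like only for Loxacon versus placebo. If the sentence was meant only as a label for completers, say so.

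Visit 2 is tied to the tenth session, which leaves its date unclear for a patient who misses sessions. The sponsor should reconcile that wording with the participation rule; no timing is proposed here.

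The change takes two or three sentences. Its cost is some extra follow-up of non-adherent patients already enrolled, and some dilution of the estimated effect by including them.

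### Two exclusion criteria reach past randomisation (NSAID change and, less clearly, hyaluronic acid), and the protocol does not say that affected patients are still assessed at visits 2 and 3

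*Protocol*

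**What the plan says.** The protocol's section on the course of the investigation places selection at the first visit: "1st visit: selection, filling in questionnaires". Visit 2 follows the tenth physiotherapy session, at about 5 weeks. Visit 3 is described as "3rd visit: Uniformly after another 2 months of taking Loxacon, in all three groups, completing questionnaires".

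Two items under Exclusion Criteria have a part that looks back from entry and a part that runs into the trial:

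- NSAID item: "NSAID changed within 3 months prior to treatment or during treatment, or" (the item then goes on to chondroprotective treatment).
- Hyaluronic acid item: "Intra-articular hyaluronic acid treatment within 6 months or such treatment during the examination".

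Other timed items in the same list, such as those on corticosteroid injection, previous physiotherapy, knee surgery and knee injury, are limited to a period before entry.

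Three further statements bear on the point. One arm is "35 people only for physical therapy", so it takes no capsule in the first 5 weeks. After that, "After the first 5 weeks, all three branches will receive enough Loxacon capsules for 2 months". On analgesics, the protocol says "If it is necessary to take painkillers, paracetamol can be used uniformly, which is recorded".

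**The concern.** An unplanned NSAID change or injection after allocation cannot be known at visit 1. If a clause about it stands as an exclusion criterion, a centre may take it as a reason to stop seeing a patient who has already been randomised.

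A change of NSAID plausibly reflects how much pain the patient has, and pain is part of the primary objective. Leaving follow-up for that reason would therefore depend on the outcome. If the rate or the reasons differed between arms, the patients remaining would no longer be comparable as randomised.

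This is a matter of trial conduct and not only of analysis. An analysis plan can define who is analysed, but it cannot restore questionnaires and goniometer readings that were never taken. Different clinics may also read the clause differently.

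**Working it through.** **1. The texts side by side.**

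| Question | What the protocol gives |
|---|---|
| When is eligibility decided? | Visit 1 |
| What period do the two items cover? | Before entry, and also during the trial |
| What happens to a randomised patient who meets the later part? | Not stated; there is no withdrawal rule tied to these events |
| Is the patient still seen at visits 2 and 3? | Not stated; the visit 3 line sets timing and the common Loxacon phase |
| Is the event recorded? | Recording is stated for paracetamol only |

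**2. The plan's own figure.** 3 × 35 = 105 patients; 3 × 7 = 21 per clinic; 105/21 = 5 clinics (implied, not stated). The total reproduces. The protocol gives no alpha, power, effect size or expected loss, so every rate below is an assumption.

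**3. Model.** Let Y be the outcome with SD 1, higher meaning worse. A removal score is Z = ρY + √(1−ρ²)·e, with e independent standard normal. A patient is removed if Z exceeds a threshold. If a fraction q of an arm is removed and z is the normal quantile of 1−q, the mean of those who stay improves by ρ·φ(z)/(1−q).

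Worked case, 15% vs 5% removed, ρ = 0.5:

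- q = 0.15: z = 1.036, φ = 0.2332, shift = 0.5 × 0.2332/0.85 = 0.137 SD
- q = 0.05: z = 1.645, φ = 0.1031, shift = 0.5 × 0.1031/0.95 = 0.054 SD
- Difference: 0.137 − 0.054 = 0.083 SD

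**4. Open comparison (physiotherapy only vs a capsule arm), no true effect.** 35 per arm before removal, two-sided t test at 0.05, 200,000 simulated trials per case.

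| Removed | About, of 35 | Shift, ρ = 0.2 | Shift, ρ = 0.5 / 0.8 | Type I error, ρ = 0.5 / 0.8 |
|---|---|---|---|---|
| 6% vs 3% | 2 vs 1 | 0.01 SD | 0.028 / 0.045 SD | 5.2 / 5.3% |
| 10% vs 5% | 3.5 vs 1.75 | 0.02 SD | 0.043 / 0.069 SD | 5.3 / 6.0% |
| 15% vs 5% | 5 vs 2 | 0.03 SD | 0.083 / 0.133 SD | 6.3 / 8.7% |

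At ρ = 0.2 the type I error is 5.0–5.2% throughout.

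**5. Blinded pair (Loxacon vs placebo).** With no true effect and equal rates and reasons there is no shift, and type I error stays at about 5.0%. With an assumed true effect of 0.50 SD and the same removal threshold in both arms, the Loxacon removal rate is 1 − Φ(z + 0.5ρ), where z belongs to the placebo rate:

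| Placebo removed | Loxacon removed, ρ = 0.5 / 0.8 | Expected estimate | Power |
|---|---|---|---|
| 5% | 2.9 / 2.0% | 0.480 / 0.453 SD | 50.9 / 48.8% |
| 10% | 6.3 / 4.6% | 0.468 / 0.425 SD | 47.9 / 44.7% |
| 15% | 9.9 / 7.5% | 0.460 / 0.404 SD | 45.4 / 41.2% |

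With nobody removed, power is 54.1%. Part of the fall is simply fewer patients: losing 10% vs 6.3% at random already lowers power to about 50%, so selection at ρ = 0.5 adds only some 2 points.

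**The case against.** The strongest reply is that the protocol never says these patients are removed. The later clauses may be meant as a question at visit 1 about treatment already planned, or as a ban on concomitant treatment put in the wrong list. The English is evidently translated, and the hyaluronic acid wording is the weaker of the two. This stands: what the text supports is a clause that excludes if read literally and whose consequence is undefined. It does not support a finding that randomised patients will be dropped. The NSAID wording is plain, however, and neither alternative reading is written down for the centres.

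It also stands that the simulation assumes removal rises with worse outcome. An NSAID may be reduced after improvement, so the direction is in general unknown and mixed reasons would weaken the correlation. Recorded paracetamol offers another outlet for pain, and all arms take Loxacon after 5 weeks. Both limit the effect.

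Two stronger readings are tempting and fail. First, a reader might infer a contradiction with the rule that "The test is completed by patients who participated in more than 70% of the treatment". That rule can be one necessary condition among several, so a patient may satisfy it and still be excluded on another ground. Second, a reader might ask whether the clause on later changes also governs chondroprotective treatment. That doubt rests on a line break in translated text and carries no weight.

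Which arm such patients are analysed in can be left to a statistical analysis plan that is not shown, and is not part of this point.

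**Conclusion.** The point holds as a defect of trial conduct. Under Exclusion Criteria, the NSAID item plainly covers events after allocation and the hyaluronic acid item less plainly so, and follow-up of the patients concerned is not fixed.

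Bias arises only if centres act on the literal reading and stop follow-up, and if removal is then related to outcome at different rates or for different reasons between arms. This is most plausible at visit 2 for the physiotherapy-only arm. Across the assumed scenarios the shift runs from about 0.01 to 0.13 SD and type I error from about 5% to 9%; the top of both ranges needs 15% vs 5% removed and a correlation of 0.8. The blinded pair shows no inflation when rates and reasons are equal.

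None of these rates or correlations comes from the protocol. The effect is probably small, and severity is minor to moderate.

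**What to change.** 1. Limit the two exclusion criteria to facts known before randomisation, including treatment already planned at visit 1.
2. Move the wording about later events to a concomitant-treatment section.
3. State there that such events are recorded with date and reason, and that the patient still attends visits 2 and 3.

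The cost is moved wording and about two added sentences. The downside is that some outcomes will be measured under changed background therapy; the recorded date and reason allow an analysis to take account of this. No rule on which treatments are allowed is proposed here; that remains a clinical decision.
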